8.3. The proportion of index patients and HHC that showed improved psychosocial functioning in the intervention arm as compared to the enhanced usual care (EUC) arm. 10	
8.4. The association between the time to transmission and clinical symptoms of the index cases.....	10
8.5. The symptomatic/asymptomatic ratio among transmitted SARS-CoV-2 in household contacts	10
8.6. The incidence of SARS-CoV-2 transmitted to HHC of the index COVID19 cases over a 4 week period, stratified by COVID-19 wave.....	10
8.7. Analysis of household exposure to SARS-CoV-2 at baseline using the baseline serology result, and development of antibodies using the serology result during follow-up. 10	
8.8. Process Evaluation Analysis.....	11

1. ***INTRODUCTION***

This Statistical Analysis Plan (SAP) describes the statistical methods to be used during the analysis and reporting of data collected for the TRACE study. This SAP should be read in conjunction with the Study Protocol (dated 15 December 2020), Case Report Forms (CRFs, Final Versions, dated 4 November 2020) and Data Management Plan (DMP, dated 18 June 2020).

2. ***OBJECTIVES OF THE STUDY***

2.1. **Primary objectives**

1. To measure frequency and timing of transmission of SARS-CoV-2 to household contacts.
2. To investigate the effect of an intensive infection mitigation intervention (STOPCOV) administered by lay health care workers on the household transmission of SARS-CoV-2.

[figure not shown]
2.2. **Secondary objectives**

1. To investigate the effect of the STOPCOV intervention on clinical outcomes and psychosocial functioning
2. To investigate the difference in transmission of SARS-CoV-2 to HHC stratified by COVID-19 wave (first or second wave)
3. To describe the household exposure to SARS-CoV-2 at baseline using the baseline serology result, and development of antibodies using the serology result during follow-up.
4. To assess acceptability, feasibility and contextual factors impacting intervention delivery (process evaluation), specifically:
 - a. To understand the acceptability and feasibility of the STOPCov intervention.
 - b. To understand how context shapes implementation of the STOPCov intervention at the level of households and individuals.
 - c. To provide explanations for observed trends in the trial findings.
 - d. To generate theoretical generalisations of how to optimise wider implementation of the STOPCov intervention to other households to reduce transmission of COVID-19.

3. ***DESIGN OF THE STUDY***

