Overview

A cluster randomised controlled study with longitudinal follow up of SARS-CoV-2 infection in 120 households which have newly diagnosed positive cases. The index cases and their HHC will be invited and enrolled after informed consent. Baseline surveys and SARs-CoV-2 screening (PCR and IgM/IgG serology) and then weekly SARs-CoV-2 screening (PCR and serology) of HHC will occur at 0, 1, 2, 3 and 4 weeks. The households will be randomized to an intensified COVID19 infection mitigation intervention (n=60) administered by CHWs vs the standard messaging (n=60). Please see Figure 1 for a schematic overview of the study design.

EUC = enhanced usual care

Figure 1: Flow chart and schematic overview of the study design.

Sample Size Determination

We calculated the different effect sizes (Table 1). Based on exponential test for comparing hazards, assuming $120*6=720$ subjects, different intraclass correlation coefficients (ICCs) and comparing $R_0=2.5$ (with resulting incidence of 0.208 among 720 subjects) to a reduced R_0 of 0.9 (64% reduction, with resulting incidence of 0.075 among 720 subjects) or 1.25 (50% reduction) or 1.5 (40% reduction).

Table 1: ICC calculations

ICC	R0 2.5 to 0.9	R0 2.5 to 1.25	R0 2.5 to 1.5
	64% reduction	50% reduction	40% reduction
0.05	1.00000	1.00000	0.999944
0.25	1.00000	0.999891	0.991312
0.50	0.999993	0.995042	0.935880
0.75	0.999729	0.972942	0.846222
0.90	0.999033	0.951485	0.792745

Randomization and stratification

After completing consent, households will be randomised in a 1:1 ratio in blocks of 10 (60 households per group; 360 patient and household contacts per group).

Overview of data and data sources for analysis

All data are collected with two individual identifiers: study ID and PID (Western Cape Government health number). The exception is data source #4, which only uses PID.

1. Redcap database
 - a. Baseline survey of index patient and household characteristics (demographics, COVID-19 symptoms, household tracing information, home/dwelling characteristics that impact transmission (size, rooms, ventilation, access to safe water, laundry facilities))
 - b. Uptake of infection control measures at all follow-up contacts (assessment of use of isolation measures and cleaning of household surfaces up to 10 days post case of last diagnosis in household, at 1, 2, 3, 4 weeks).

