4. STUDY OUTCOMES

4.1. Primary study outcomes

- The incidence rate of SARS-CoV-2 infections among HHC of the index COVID19 cases over a 4 week period
- The time to transmission to HHC during that time period
- The association between the time to transmission and clinical symptoms of the index cases
- The symptomatic/asymptomatic ratio among transmitted SARS-CoV-2 in household contacts
- The proportion of transmissions to HHC in the enrolled households of COVID cases assigned to the infection mitigation intervention arm compared with the households in the enhanced usual care (EUC) arm.

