5. GENERAL PRINCIPLES OF ANALYSIS

The statistical analysis plan will be finalised and signed-off prior to database lock. Post-hoc analysis (analyses performed that are different from those described in the final version of the SAP) will be documented in the final report.

Descriptive summaries will be presented using summary statistics (e.g. number (n), mean, standard deviations (SD), median, minimum, maximum) and 95% confidence intervals (CI) for continuous parameters or frequency distributions (n, %) for categorical parameters.

In general, all households who entered the study will be included in the statistical evaluation (intention-to-treat analysis). Households who completed the final screening will be included in the per-protocol analysis. There will be no predefined interim statistical analysis or stopping rules.

All output will be generated using STATA SE Version 13 or R. No missing data will be replaced, and it will be shown in any summaries as missing.

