7. ANALYSIS OF PRIMARY STUDY OUTCOMES

7.1. The proportion of SARS-CoV-2 transmitted to HHC of the index COVID19 cases over a 4 week period

SARS-CoV-2 infection in a HHC will be defined as a positive PCR or evolving positive serologic test in a HHC who had a negative PCR or negative serology at baseline. The incidence of SARS-CoV-2 infection in HHC will be calculated as the number of new cases divided by the person time at risk and 95% confidence intervals calculated based on the Poisson distribution adjusted for clustering by household. This incidence as well as the timing to transmission will be analysed using exponential shared frailty models taking the clustering by household into account and allowing for censoring. The start time will be the date of diagnosis of the index case and the event time the date of diagnosis of the HHC using the date of the first positive test based on PCR or serology. Models will include possible confounders including adjustment for baseline values.

7.2. The proportion of transmissions to HHC in the enrolled households of index COVID cases assigned to the infection mitigation intervention arm compared with the households in the enhanced usual care (EUC) arm.

The incidence of SARS-CoV-2 will be estimated for the different study arms and incidence of and timing to SARS-CoV-2 per study arm will be compared by including study arm in the exponential frailty models.

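### The constant-hazard frailty model in SAP 7.1–7.2 cannot show when household transmission occurs, a primary outcome; its clock and at-risk rule also need aligning

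*SAP*

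**What the plan says.** Primary objective 1 (SAP 2.1) is "To measure frequency and timing of transmission of SARS-CoV-2 to household contacts". SAP 4.1 lists as a primary outcome "The time to transmission to HHC during that time period".

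SAP 7.1 analyses incidence and timing together with exponential shared frailty models that account for household clustering and allow for censoring. The clock is given as: "The start time will be the date of diagnosis of the index case and the event time the date of diagnosis of the HHC". A new infection is "a positive PCR or evolving positive serologic test in a HHC who had a negative PCR or negative serology at baseline". For the arms, SAP 7.2 says incidence and "timing to SARS-CoV-2 per study arm will be compared by including study arm in the exponential frailty models".

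The SAP section 3 overview says screening "of HHC will occur at 0, 1, 2, 3 and 4 weeks". SAP 6.1 will summarise the time from the index positive test to enrolment, so the plan recognises a gap but gives no length. The sample size section uses a control incidence "with resulting incidence of 0.208 among 720 subjects".

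The SAP names no Kaplan-Meier, piecewise or interval-censored analysis of infection. The weekly profiles in 8.7 concern serology only.

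**The concern.** **Main point: shape.** An exponential model has one rate and no parameter for whether infections cluster early or late. Adding a household frailty lets the population hazard fall only because high-risk households are used up first. Infection dates therefore reach the fitted weekly pattern only indirectly. If transmission is mostly early, and so perhaps over before an intervention can act, the planned model would not show it.

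**Secondary point: clock and at-risk set.** Time runs from index diagnosis, but a contact qualifies by a test at the later baseline visit. If only contacts negative on both tests can become cases, the days before baseline are event-free by construction and still enter the denominator. If one negative test is enough, as the text literally says, a PCR-positive, seronegative contact can be an event at baseline although infected before randomisation. The two readings bias the modelled absolute rate differently.

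**Working it through.** **Inputs.** The plan's 0.208 reproduces as 2.5 × 60/720 = 0.2083, and its 0.075 as 0.9 × 60/720. R0 1.5 on the same scale gives 0.125. Spreading R0 2.5 over six contacts would give 2.5/6 = 0.417, and R0 1.5 would give 0.25. I use 0.208 and 0.417 as assumed 4-week control risks p. The documents give no lag, frailty variance or weekly infection pattern; those below are assumptions.

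**1. Weekly pattern implied by the model.** With gamma frailty variance θ, the population survival is S(t) = (1 + θHt/28)^(−1/θ), with H set so that 1 − S(28) = p. The share of infections in week k is [S(7(k−1)) − S(7k)]/p. At p = 0.208:

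- No frailty: S(t) = exp(−ht), h = −ln(0.792)/28 = 8.33 per 1000 person-days. Weekly shares are 27/26/24/23%.
- θ = 1: H = 0.2626, S(7) = 1/1.0657 = 0.938, week-1 share 30%.
- θ = 4: H = 0.3854, S(7) = 1.3854^(−1/4) = 0.922, week-1 share 38%.

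No infection date enters these figures. At p = 0.417 the week-1 share is 30%, 36% and 56% for θ = 0, 1 and 4. The curve can bend further there, but through household variance.

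**2. Fitting the model to different true patterns.** Simulation: 120 households of 6, θ = 1, events dated at weekly visits, no lag, 200 trials per pattern and risk. The early pattern has weekly shares of 66/23/8/4%; the others are even and the reverse. Median fitted week-1 share:

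| True week-1 share | Exponential frailty, 0.208 | Exponential frailty, 0.417 | Visit-interval terms, 0.208 | Visit-interval terms, 0.417 |
|---|---|---|---|---|
| 66% | 30% | 36% | 66% | 65% |
| 25% | 29% | 33% | 25% | 25% |
| 4% | 28% | 31% | 4% | 4% |

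A separate simulation used hazard shares 55/30/10/5, a 2-day gap and risk 0.417. Observed cumulative control risk at weeks 1–4 was 0.190/0.262/0.284/0.294. The exponential frailty fit, even with delayed entry, gave 0.122/0.213/0.284/0.341. That puts 36% of events in week 1 (0.122/0.341) against 65% observed (0.190/0.294).

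**3. Clock, both tests negative.** A contact contributes on average p/h days after baseline (24.98 at 0.208, 21.64 at 0.417) plus L event-free days. The fitted rate is p/(p/h + L). At 0.208 and L = 7: 0.208/31.98 = 6.51 against 8.33 per 1000, which is 22% too low.

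| Lag L (days) | 1 | 2 | 3 | 5 | 7 |
|---|---|---|---|---|---|
| Too low, p = 0.208 | 4% | 7% | 11% | 17% | 22% |
| Too low, p = 0.417 | 4% | 8% | 12% | 19% | 24% |

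**4. Clock, literal 'or'.** Let q be the share of contacts PCR-positive and seronegative at baseline. The rate is [q + (1−q)p]/[L + (1−q)p/h], which is unbiased at q = hL. That is 0.8% to 5.8% for 1–7 days at 0.208, and 1.9% to 13.5% at 0.417. Above this the bias is upward. If q is exactly the share infected during the lag at constant hazard, 1 − exp(−hL), the bias is −0.02% to −0.65% at 0.208 and −0.04% to −1.7% at 0.417.

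**5. Arm hazard ratio.** With both tests negative, equal lags and constant hazard, ln(0.875)/ln(0.792) = 0.573 becomes at most 0.579. At 0.417 against 0.25, 0.533 becomes at most 0.548. In the front-loaded simulation, omitting delayed entry moved the fitted ratio by about 0.03 (0.462 to 0.489 at a 2-day gap). Under the literal 'or', with every infection between index diagnosis and baseline counted, the ratio was 0.61–0.66 against a true 0.573 (constant hazard) and 0.55–0.78 against 0.533 (front-loaded).

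**The case against.** **Timing may be described anyway.** SAP section 5 says "Descriptive summaries will be presented using summary statistics", including median, minimum and maximum. Applied to observed infection times, these would tell early from late. That is fair, but the provision is generic and not tied to this outcome. It yields no weekly infection curve and no cluster-adjusted interval. The true patterns in step 2 are also invented; they show what the model can return, not what will happen.

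**The lag bias is conditional.** A reader might infer that the modelled rate is certainly too low. The SAP writes 'or', and under that reading steps 3 and 4 together leave size and sign open. The SAP is silent on delayed entry and does not exclude it. This objection stands, which is why the clock comes second.

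**The arm comparison.** A reader might infer that the randomised contrast fails. Step 5 does not support that for equal lags and a both-negative at-risk set; unequal lags were not examined. Nor is a single arm coefficient itself the fault, because the model proposed below also has one. The fault is reading that coefficient as a comparison of timing.

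**Crude incidence.** SAP 7.1 also plans cases over person-time at risk with Poisson intervals. Its time origin is not stated, and no claim is made about it.

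**Origin.** Index diagnosis is a natural origin for relating transmission to the index case's symptoms (SAP 4.1 and 8.4). It can be kept.

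**Conclusion.** The main point holds. As specified, the model for timing, a primary outcome, returns a week-1 share of about 27–30% at risk 0.208 for frailty variance 0–1, and up to about 38% at variance 4, largely whatever the true pattern. This follows from the constant hazard; only the size of the contrast rests on assumed patterns.

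The secondary point holds as an unresolved definition. The understatement of the modelled rate by 4–24% needs both tests negative and an assumed lag of 1–7 days. Under the literal wording the bias may be close to zero or upward, depending on a baseline share that the documents do not give.

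The harm falls on the timing results and the modelled absolute rate. The SAP should be amended before it is signed off.

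**What to change.** **Timing.** In SAP 7.1–7.2, replace the constant baseline hazard with visit-interval terms for weeks 1–4 (piecewise exponential or complementary log-log), plus arm and a household random effect. Merge adjacent intervals if a pooled interval has no events; in the simulations a pooled week was empty in at most 0.5% of trials. Report weekly and cumulative 4-week infection proportions by arm with cluster-adjusted intervals. State that the arm coefficient compares hazard overall and that any comparison of timing between arms is descriptive. A full arm-by-week interaction is too sparse: at 0.208 the early pattern leaves about 360 × 0.208 × 0.04 = 3 control and 360 × 0.125 × 0.04 = 2 intervention events in week 4.

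*Cost:* three extra parameters and some change in precision. The SD of the log hazard ratio was 0.25–0.28 with interval terms against 0.22–0.29 for the exponential model at 0.208, and 0.24–0.25 against 0.17–0.22 at 0.417. The ratio of median estimate to SD stayed within about 6%.

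**Clock.** Define one at-risk set, negative on both tests at baseline, and report baseline positives separately by arm. Count risk time only from the baseline test, either by starting the clock there or by keeping index diagnosis as origin with entry at baseline. Report the diagnosis-to-baseline lag by arm; SAP 6.1 already plans a summary of the time to enrolment.

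*Cost:* a smaller at-risk set, by a number the documents do not give, and transmission before baseline described only through the baseline positives.

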8. ANALYSIS OF SECONDARY STUDY OUTCOMES

8.1. The proportion of index patients and HHC that were hospitalised for COVID-19 during the period of follow-up in the intervention arm as compared to the enhanced usual care (EUC) arm.

The binary outcome of hospitalisations for COVID-19 will be determined for the different study arms will be compared and analysed using a mixed effect logistic regression model.

8.2. The proportion of deaths in index patients and HHC due to COVID-19 during the period of follow-up in the intervention arm as compared to the enhanced usual care (EUC) arm.

The binary outcome of deaths in index patients and HHC for COVID-19 will be determined for the different study arms and will be compared and analysed using a mixed effect logistic regression model.

8.3. The proportion of index patients and HHC that showed improved psychosocial functioning in the intervention arm as compared to the enhanced usual care (EUC) arm.

The continuous outcome of psychosocial functioning in index patients and HHC for COVID-19 will be compared and analysed using linear regression.

8.4. The association between the time to transmission and clinical symptoms of the index cases

The incidence of transmitted SARS-CoV-2 infections to household contacts will be estimated and compared by the number and duration of clinical symptoms of the index patients. These symptom characteristics can also be included in the frailty models.

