Process: Newly diagnosed SARS-CoV-2 index patients will be identified and recruited from a mobile clinic and local community clinics conducting SARS-CoV-2 testing. Index cases and their households will be invited to enroll. After enrolment, the household will be randomised to the infection mitigation intervention or enhanced usual care messaging. Baseline demographic, household characteristics questionnaire will be administered, and each household occupant invited to participate. Following consent procedures, household contacts (HHC) will be screened at baseline and weekly for 4 weeks for evidence of COVID infection. Specifically, the research team will conduct SARS-CoV-2 GeneXpert PCR testing and antibody serology. They will collate self- administered daily symptom checks on a weekly basis. Six months after a positive SARS-CoV-2 antibody, the study nurse will visit the participant household to conduct SARS-CoV-2 serology to assess for the presence of antibodies.
Duration: We will recruit 120 households over 1-3 months. We will initiate a prospective longitudinal follow up of the household contacts of each case for 4 weeks in each case.
Analysis: Calculate proportion of SARS-CoV-2 transmission from index cases in each household over 4- week period. Describe the proportion of symptomatic and asymptomatic SARS-CoV-2 infection in a high density, low resourced community. Investigate the impact of the infection mitigation intervention by comparing Ro number in households randomised to intervention vs standard of care. Secondary outcomes for the trial will include clinical outcomes (hospitalisations, death), linkages to care for people, psychosocial functioning and stigma.

Background

South Africa currently has the largest COVID19 epidemic in Africa, with >205,721 cases reported in all nine Provinces (*COVID-19 South African Coronavirus News and Information Portal*, n.d.). The South African Department of Health has reported more than 3310 deaths of individuals infected with severe acute respiratory syndrome coronavirus-2 (SARS-CoV-2), the cause of coronavirus disease (COVID-19) to date (Karim, 2020). As screening and testing is scaled up, South African healthcare facilities are preparing for the mitigation stage in the epidemic, wherein people with severe COVID-19, mostly adults, may require hospitalization, and intensive care (Karim, 2020).

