Overall Objective: The overarching objective of this protocol is to understand and mitigate household transmission of SARS-CoV-2 infection in a low income, high-density community setting. Data over an 8-month period will be used to determine the Ro for SARS-CoV-2 infection, the rate of symptomatic disease and the impact of a lay health care worker administered infection mitigation intervention (STOPCOV) in low income, high-density communities in South Africa.

Specific Aim 1: To measure frequency and timing of transmission of SARS-CoV-2 to household contacts. The proportion of patients and household contacts who have symptoms vs asymptomatic disease will also be measured.

Specific Aim 1 Endpoints: SARS-CoV-2 transmission will be monitored using nasopharyngeal swabs for SARS-CoV-2 PCR and serology (IgM/IgG) assays in all HHC weekly for 1 month. Symptom checklists will be completed daily and collated weekly for each HHC.

Specific Aim 2: to investigate the effect of an intensive infection mitigation intervention known as STOPCOV administered by lay health care workers, compared with enhanced usual care, on SARS-CoV-2 household transmission.

Specific Aim 2 Primary Endpoint: The proportion of transmissions to HHC in the households of COVID cases assigned to the infection mitigation intervention arm compared with the households in the enhanced usual care (EUC) arm.

Population and Sample: We will consecutively recruit n=120 SARS-CoV-2 positive index patients 12 years and older. The index patients will be identified from referrals from associated public sector clinic screening in a high-density community in Cape Town. Each household is estimated to have 6-8 occupants. We will invite HHC (n=~6-8) household contacts of each of the index patients (n=~720).

Duration: The study will be conducted for eight months from June 2020 and last until Jan 2021.

[figure not shown]

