4.2. Secondary Outcomes

- The proportion of index patients and HHC that visited a primary health clinic during the period of follow-up in the intervention arm as compared to the enhanced usual care (EUC) arm.
- The proportion of index patients and HHC that were hospitalised for COVID-19 during the period of follow-up in the intervention arm as compared to the enhanced usual care (EUC) arm.
- The proportion of index patients and HHC that died due to COVID-19 during the period of follow-up in the intervention arm as compared to the enhanced usual care (EUC) arm.
- The proportion of index patients and HHC that showed improved psychosocial functioning, defined as lower GHQ 12, UCL loneliness scores and Stigma scores, in the intervention arm as compared to the enhanced usual care (EUC) arm.
- The proportion of SARS-CoV-2 transmitted to HHC of the index COVID19 cases over a 4 week period, stratified by COVID-19 wave.
- The proportion of index patients and HHCs who developed antibodies during follow-up.
- Process Evaluation Outcomes:
 - Barriers and facilitators to implementation of the STOPCov intervention.
 - Identified contextual patterns within households that interact with the implementation of STOPCov intervention
 - Theoretical explanations of how different structural relations and mechanisms impact on intervention delivery and outcomes.
 - Generalizable inferences and predictions on how best to optimise the STOPCov intervention.

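### COVID-19 hospitalisation and death are compared over index patients and contacts together, with no role term or by-role report, so an effect cannot be traced to prevented infection or to a changed course of illness

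*SAP*

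**What the plan says.** SAP 4.2 defines three care outcomes over both kinds of participant: clinic visits ("The proportion of index patients and HHC that visited a primary health clinic during the period of follow-up in the intervention arm"), COVID-19 hospitalisation and COVID-19 death, each compared with enhanced usual care.

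SAP 8.1 gives the hospitalisation analysis. Its outcome is "The proportion of index patients and HHC that were hospitalised for COVID-19 during the period of follow-up in the intervention arm", set against enhanced usual care, and the arms are compared by mixed-effects logistic regression. SAP 8.2 does the same for death: "The binary outcome of deaths in index patients and HHC for COVID-19 will be determined for the different study arms", again with a mixed logistic model. Neither section names a covariate, a random effect, an interaction or a table by participant role. The sentence on confounders and baseline adjustment stands in SAP 7.1 and covers the transmission models only. SAP section 8 has no analysis of clinic visits.

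On who is pooled, the Protocol (Population and Sample) says: "We will consecutively recruit n=120 SARS-CoV-2 positive index patients 12 years and older". Households are randomised after enrolment (Protocol, Setting and population), so every index patient is infected by then. Contacts are tested from week 0 and may be infected already, become infected later, or never be infected.

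The Protocol schema (Analysis row) adds: "Secondary outcomes for the trial will include clinical outcomes (hospitalisations, death), linkages to care for people, psychosocial functioning and stigma". The SAP has no outcome called linkage and does not say that clinic visits measure it.

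**The concern.** The intervention has different routes to benefit in the two roles. In an index patient it can change only what follows an infection that has already happened. In a contact who is still uninfected it can also stop the infection, which is the trial's main aim. A single arm effect over both roles averages these routes, with weights set by how many events each role supplies.

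The household random effect, if that is what the SAP intends, does not help, because role varies within every household. A reader shown only the pooled odds ratio could not tell fewer infections among contacts from milder illness or different care-seeking among people already ill. Those two findings would lead to different conclusions about what STOPCOV does.

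**Working it through.** **1. The plan's own figures.** The documents give no event rate for hospitalisation, death or clinic visits. They do give transmission figures (Protocol, Statistical Analysis and sample size; SAP section 3), and these reproduce: 60 households × 2.5 = 150 and 150/720 = 0.208; 60 × 0.9 = 54 and 54/720 = 0.075. So 0.208 is the cases of 60 households divided by the people of 120. Divided by one arm's 360 people, the figure is 150/360 = 0.417. Both values are carried below.

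**2. Infected people per arm, R0 2.5 versus 1.5.**
- EUC: 60 index + 60 × 2.5 = 60 + 150 = 210.
- STOPCOV: 60 index + 60 × 1.5 = 60 + 90 = 150.
- Fall in contacts: 1 − 90/150 = 40%.
- Pooled fall, with equal severity per infection (assumed) and no effect in index patients: 1 − 150/210 = 28.6%.

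**3. Odds ratios.** The risk of hospitalisation per infection, h, is assumed to be 2% to 10%. Index events per arm are 60h, multiplied by an assumed index risk ratio under STOPCOV. Contact events are (contacts × incidence × h), multiplied by 0.6 under STOPCOV.

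One case in full: h = 5%, 300 contacts per arm, incidence 0.417, no index effect. Control events are 3 + 6.25 = 9.25 of 360; intervention events are 3 + 3.75 = 6.75 of 360. The pooled odds ratio is (6.75/353.25)/(9.25/350.75) = 0.725, against 0.595 in contacts.

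Ranges over h and both incidences, 300 contacts per arm:

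| Index risk ratio (assumed) | Contact OR | Pooled OR |
|---|---|---|
| 0.6 | 0.59–0.60 | 0.59–0.60 |
| 1.0 | 0.59–0.60 | 0.72–0.80 |
| 1.5 | 0.59–0.60 | 0.89–1.04 |
| 2.0 | 0.59–0.60 | 1.06–1.30 |

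The Protocol can also be read as about 360 contacts per arm. Allowing for that, the null-index range is 0.70–0.80. At a 64% reduction with no index effect, the contact OR is 0.35–0.36 and the pooled OR 0.53–0.67.

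Index patients are 14–17% of participants (60/420 to 60/360). Under equal severity they supply 29–49% of control-arm events (60/210 to 60/122.4, where 122.4 = 60 + 300 × 0.208). That share is why the index effect weighs so heavily in the pooled figure.

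**4. How many events there would be.** Control-arm index events: 60 × 0.02 = 1.2 to 60 × 0.10 = 6. Control-arm contact events: 300 × 0.208 × 0.02 = 1.2 to 360 × 0.417 × 0.10 = 15. With a two-sided 5% test of two proportions (assumed) and no allowance for clustering, power for a 40% reduction is about 5–24% in contacts alone and 4–17% pooled.

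**5. Clinic visits.** Suppose STOPCOV raises visits per infected person by 20% (assumed) and cuts contact infections from 150 to 90. In units of one infected EUC person's visit rate, infected people contribute 210 under EUC and 1.2 × 150 = 180 under STOPCOV. STOPCOV also has 60 more uninfected contacts. If they visit at relative rate b, the difference is −30 + 60b: a 14% fall (30/210) at b = 0, no change at b = 0.5, and a rise above that. The pooled proportion can move either way while care per infected person improves.

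**The case against.** The pooled comparison is deliberate: the Protocol's Design section says that outcomes are assessed on index patients and their contacts. Whole households are randomised, each with one index case, so role is balanced by design and cannot confound the arm contrast. Total household admissions or deaths by arm is a coherent intention-to-treat quantity. All of this stands. Splitting by role also does not fully separate the routes, because contacts already positive at week 0 resemble index patients. With so few events, a formal arm-by-role interaction is impractical. Both limits are accepted.

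A reader might infer several stronger things that the documents do not support:
- **That pooling necessarily dilutes the effect in contacts.** It does so only if the index effect is nearer the null, and the documents give no index effect. The intervention supports the whole household, so a similar relative effect in both roles is possible, and then nothing is diluted.
- **That dilution is worse because index patients are sicker.** If they were 2 or 3 times as likely to be admitted, the pooled fall would be 1 − 210/270 = 22.2% or 1 − 270/330 = 18.2%. The arithmetic is right, but nothing in the documents supports those ratios, and index patients must be self-isolating at home at diagnosis.
- **That role is the strongest baseline predictor.** The documents do not show this. The severity predictors they name are age and chronic conditions.
- **That a pooled odds ratio is planned for clinic visits.** SAP section 8 plans no analysis of them.
- **That clinic visits in index patients are the linkage measure.** No document says so. SAP 4.2 does not restrict visits to COVID-19, unlike its hospitalisation and death outcomes.

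**Conclusion.** The concern holds as a gap in modelling and reporting; the pooled estimate is not biased by it. SAP 8.1 and 8.2 give one arm effect over two roles and plan nothing that would show where that effect arises.

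The size depends on the index effect, which is unknown. If it is null, a 40% fall in contacts appears as about 29% pooled, or an odds ratio near 0.60 appears as 0.70–0.80. If both roles share the relative effect, there is no loss. If index admissions rose by half or doubled, the pooled odds ratio would approach or pass 1. These figures rest on the plan's R0 values, equal severity per infection, and an assumed 2–10% hospitalisation risk per infection.

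Power is low either way, so reporting by role makes the result interpretable rather than conclusive. The pooled clinic-visit proportion should not be read as evidence on linkage to care.

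**What to change.** - **SAP 8.1 and 8.2:** keep the pooled arm estimate. Add participant role (index or contact) as a covariate and name household as the random effect.
- **New table:** give hospitalisation, death and clinic visits by arm within index patients and within contacts, with contacts split by infection status at baseline. State that role-specific effects are descriptive unless event counts allow modelling.
- **Clinic visits:** say in SAP section 8 how this outcome will be summarised, and that the pooled proportion is not evidence on linkage to care. If linkage is to remain an outcome, it needs its own definition and denominator in the SAP.

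The cost is SAP wording and some extra tabulation. Role is known for everyone and contacts are tested at week 0, so no new data are needed. The downside is that role-specific figures will rest on few events and have wide intervals.
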